9.1.1 Nausea, Vomiting, and Diarrhea

Participants with Grade 1 or 2 nausea, vomiting, or diarrhea may be treated symptomatically with hydration, oral antiemetic therapies or antiemetic suppositories at the discretion of the site investigator or designated clinical staff. The site investigator should order any clinically relevant laboratory analyses (per judgment of the site investigator/or designee). Participants should be reminded to take study drug with food.

Participants with Grade ≥ 3 nausea, vomiting, or diarrhea, for which an alternative etiology is not established, must discontinue the study drug temporarily until grade 2 or lower and be treated symptomatically. Should condition(s) not improve to Grade <2 within 7 days, the site investigator/designee should consult the PSRT for guidance on continuing the temporary discontinuation or progressing to permanent discontinuation of study drug. Repeat episodes of these events will be handled independently, and the instruction above will be followed for each event.

9.1.2 Management of ALT/AST Elevations

All study participants will either be immune to HBV at study entry, or will receive HBV vaccination. Therefore, HBV infection is not likely to be a cause of AST/ALT elevations.

Careful assessments should be done to rule out the use of alcohol, lactic acidosis syndrome, non-study medication-related drug toxicity, herbal medications/supplements, or viral hepatitis as the cause of elevation in AST or ALT of any grade. The participant must be carefully assessed for any symptoms or signs of hepatotoxicity, including fatigue, malaise,

anorexia and nausea, jaundice, acholic stools, right upper quadrant pain, or hepatomegaly. If the AST/ALT elevation is considered most likely to be due to concomitant illness or medication, standard management, including discontinuation of the likely causative agent, if possible, should be undertaken. If symptoms or signs of clinical hepatitis are present, study drug must be held or discontinued.

Grade 1 transaminase elevation:

For study participants with less than Grade 1 AST and ALT at study entry, an increase to Grade 1 AST or ALT even in an asymptomatic participant may be of concern. AST and ALT must be repeated as soon as possible (at most within 1 week of the receipt of the results). Study drug may be continued while repeating AST and ALT at the discretion of the investigator provided the participant is asymptomatic. Should the repeat AST and ALT testing indicate a continuation of Grade 1, the PSRT should be immediately consulted. In the case of symptomatic participants, study drug will be held temporarily, and management (including resumption of study drug) should be arranged in consultation with the PSRT.

Grade 2 transaminase elevation:

Participants should have AST/ALT re-checked as soon as possible (at most within 1 week of the receipt of the results) and then be followed weekly until levels are Grade < 1. The frequency of follow up may be altered at the discretion of the site investigator following consultation with the PSRT. Study drug may continue at the discretion of the investigator provided the participant is asymptomatic. In the case of symptomatic participants, study drug will be held temporarily, and management (including resumption of study drug) should be arranged in consultation with the PSRT.

Grade 3 transaminase elevation:

Study drug should be temporarily held for any Grade 3 AST or ALT. Participants should have AST/ALT re-checked as soon as possible (at most within 1 week of the receipt of the results). Participants should then be followed weekly until levels are Grade < 1. Resumption of study drug should be arranged in consultation with the PSRT.

Grade 4 transaminase elevation:

Study product should be permanently discontinued for any Grade 4 AST and/or ALT.

Appropriate care and management of the participant will be ensured.

If the investigator has determined in consultation with the PSRT that the case has stabilized, it may be possible to decrease the frequency of follow-up laboratory testing in addition to resumption of study drug.

9.1.3 Management of Creatinine Clearance

After enrollment, if the calculated creatinine clearance is less than <75ml/min, the study product should be temporarily held and confirmed within one week of the receipt of the results, and the PSRT should be consulted. If the creatinine is confirmed to be <75ml/min, the study product must be permanently discontinued.

9.1.4 Management of Hypophosphatemia

Grades 1 and 2 hypophosphatemia:

The phosphate should be repeated within 2 weeks of the receipt of any initially abnormal results. Supplemental phosphate should be given with phosphate-rich food or fluid with or without neutral phosphate solution. Other causes of phosphate loss should be evaluated.

Unless other temporary study drug hold requirements apply, study drug need not be held.

Grade 3 hypophosphatemia:

The phosphate should be repeated within 1 week of receipt of any initially abnormal results, and should be accompanied by serum creatinine testing and urine dipstick for protein/glucose. Supplemental phosphate should be given with phosphate-rich food or fluid with or without neutral phosphate solution, and other causes of low phosphate should be investigated. Participants with any of the following results (of tests accompanying the repeat phosphate test) will have study drug held:

- Proteinuria >2+
- Glycosuria >2+

- Creatinine > ULN
- Creatinine clearance <LLN

Participants may continue study drug provided that:

- Study drug hold is not otherwise indicated (e.g., due to the results of creatinine, creatinine clearance, urine protein, and/or urine glucose)
- Phosphate levels will be retested approximately weekly until return to <Grade 2, unless other retesting schedule has been advised by the PSRT

Grade 4 hypophosphatemia:

The phosphate should be repeated within 1 week of the receipt of any initially abnormal results, and should be accompanied by serum creatinine testing and urine dipstick for protein/glucose. Supplemental phosphate should be given with phosphate-rich food or fluid with or without neutral phosphate solution. Other causes of low phosphate should be investigated.

Participants will have study drug held, and the PSRT must be immediately contacted. Phosphate levels will be retested approximately weekly until return to <Grade 2, unless another retesting scheduled has been advised by the PSRT.

Participants may resume study drug, provided that:

- Study drug hold is not otherwise indicated (e.g., due to the results of serum creatinine, creatinine clearance, urine protein, and/or urine glucose)
- The phosphate level has returned to <Grade 2
- A request to resume study drug is approved by the PSRT

PSRT notification should occur for any result >Grade 2 for protein or glucose measured by urine dipstick performed at the time of confirmatory draw for a phosphate level.

9.1.5 Proteinuria

Proteinuria will be assessed by urine dipstick. A finding of 1+ proteinuria should be confirmed

with a second urine dipstick performed no earlier than one week. Proteinuria of 2+ or greater does not need to be confirmed at a separate visit. The site investigator/designee should temporarily hold study drug in the following circumstances:

- Detection of 3+ or greater proteinuria at any visit. Study drug should be held regardless of serum creatinine or phosphorus results obtained at the time of proteinuria detection. Urine dipstick testing and serum creatinine and phosphate should then be performed monthly for at least three months.
- Detection of 2+ proteinuria. Study drug should be held until results of serum creatinine results obtained at the time of proteinuria detection are available. Study drug hold should continue if hold criteria outlined for serum creatinine are met. If neither value meets criteria for study product hold, study drug should be resumed.
- Detection of 1+ proteinuria confirmed on two separate visits. Study drug should be held only if serum creatinine or phosphorus results obtained at the time of detection of proteinuria meet hold criteria.

9.1.6 Glycosuria

Glycosuria will be assessed by urine dipstick. A finding of 1+ glycosuria should be confirmed with a second urine dipstick performed no earlier than one week but no later than 2 weeks after detection of the first 1+ glycosuria. Glycosuria of 2+ or greater does not need to be confirmed at a separate visit.

The severity of glycosuria is graded using the same grading scale as for proteinuria. The site investigator/designee should temporarily hold study drug in the following circumstances:

- Detection of 3+ or greater glycosuria at any visit. Study drug should be held regardless of serum creatinine or phosphorus results obtained at the time of proteinuria detection. Urine dipstick testing and serum creatinine and phosphorus should then be performed monthly for at least three months.

- Detection of 2+ glycosuria. Study drug should be held until results of serum creatinine and phosphorus results obtained at the time of glycosuria detection are available. Study drug hold should continue if hold criteria outlined for serum creatinine and/or phosphorus are met. If neither of these values meets criteria for study drug hold, study drug should be resumed.
- Detection of 1+ glycosuria confirmed on two separate visits. Study drug should be held only if serum creatinine or phosphorus results obtained at the time of detection of glycosuria meet hold criteria.

9.2 HEPATITIS B INFECTION

Adolescents who test positive for Hepatitis B surface antigen (HBsAg) during screening, or demonstrate signs or symptoms of Hepatitis B during the study, will be referred for appropriate care. If Ag positive at screening, participants are ineligible for study participation. All HBsAB sero-negative adolescents who have no history of previous vaccination, will be vaccinated, during the screening period, 30 days after the initial injection (ideally at enrollment), and then again after 24 weeks. It is important to note that participants who are Hep B infected may incur a “Hep B viral flare” on cessation of TDF/FTC therapy. This should be monitored for and appropriately managed should it occur.

9.3 PREGNANCY

All participants will be provided with male and/or female condoms. As participants will be required to be sexually active in order to enroll in the study, females will be required to use condoms as well as take low dose, combination oral or injectable hormonal contraception, in addition to receiving contraceptive counseling throughout the duration of study participation. Pregnancy testing is performed at all study visits and participants are encouraged to report all signs or symptoms of pregnancy to study staff. The Site Investigator or designee will discontinue drug permanently, counsel any participant who becomes pregnant regarding possible risks to the fetus according to site SOPs. The Site Investigator/designee also will refer the participant to all applicable services; however, sites will not be responsible for paying for pregnancy-related care. Youth-friendly sexual reproductive health services are available free of charge at care facilities in site surrounds. A

participant who is pregnant will continue to be followed until the pregnancy outcome is ascertained but will not receive any study product.

9.4 CRITERIA FOR EARLY TERMINATION

Participants may voluntarily withdraw from the study for any reason at any time. The Principal Investigators may withdraw participants to protect their safety, and/or if participants are unable or unwilling to comply with study procedures.

9.5 TREATMENT FOR SEXUALLY TRANSMITTED INFECTIONS

Participants will be tested for HSV-2, chlamydia, and gonorrhea during screening, week 12 and at week 48.. All participants will receive screening and treatment for STIs throughout the study and their identified partners will be managed using syndromic management of STIs according to South African STI guidelines.

9.6 MANAGEMENT OF HIV INFECTION

Refer to Section 7.10.1 for specific study procedures regarding participants who become infected with HIV at any time during the study.

9.7 CRITERIA FOR DISCONTINUATION

The criteria for permanent discontinuation of further study product for an individual participant are:

- Product-related toxicity (see Section 9.1)
- Requirement for prohibited concomitant medications
- HIV infection
- Pregnancy/lactation
- Completion of study as defined in the protocol
- Request by participant to terminate study product
- Any conditions or clinical reasons that will threaten safety and well-being of participant

The criteria for premature discontinuation of further study participation for an individual participant are:

- Lost to follow up as per site SOP
- Participant repeatedly non-compliant with study product as prescribed
- Pregnancy/lactation
- Request by participant to withdraw from study
- Request of the primary guardian or caregiver if s/he thinks the study is no longer in the best interest of the participant
- Participant judged by the Site Investigator to be at significant risk of failing to comply with the provisions of the protocol as to cause harm to self or seriously interfere with the validity of study results
- At the discretion of the Independent Ethics Committee, Medicine Control Council, Site Investigator, or pharmaceutical supporter.
- DAIDS, NIAID, the Office of Human Research Protection (OHRP), and the FDA as regulatory entities may also discontinue the study at their discretion.

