Design	
The study is designed as an open-label, single arm cohort study, to evaluate the Acceptability, safety and Use of daily oral PrEP (FTC/TDF) in 150 adolescents (approximately 75 participants at each site), ages 15-19 years, their adherence to study product, and any changes in their sexual and health behaviors over a 12-month (52 week) period. All participants will complete an initial (12 week) 3- month period, during which they will receive PrEP as part of a combination prevention package. At all subsequent visits, participants will be offered the opportunity to hear real-time feedback of drug level data as part of their adherence counseling or they may choose to have adherence counseling without the feedback of drug level data. The decision about feedback as well as self reported adherence will be captured via interviewer administered questionnaires at each follow up visit. At the first 3 month (week 12) visit and 3 monthly (weeks 24, 36, 48) intervals thereafter participants will be offered the following options: full package + PrEP, stop PrEP and continue with rest of package or alternatively re-start PrEP if previously stopped. This will occur during protocol-specified study visits.
 
Participants will be followed regardless of PrEP usage for a total of 12 months (52 weeks). PrEP may be stopped at any other clinic visit but recommencement can only occur at a scheduled visit when all medical criteria are met including a negative HIV test. Adherence counselling will be offered at every visit with options to have drug level feedback or not as part of this counselling.

Study site	The study will be conducted at The Desmond Tutu HIV Foundation research site in Masiphumelele, Cape Town and the Perinatal HIV Research Unit (PHRU) site in Soweto, near Johannesburg.
Study drugs	FTC/TDF or Truvada® is a 200mg/300mg fixed dose combination tablet containing emtricitabine (FTC) and tenofovir disoproxil fumarate (TDF).
Study population	Healthy, HIV-uninfected adolescents, 15 and 19 years of age
Number of participants	150 enrolled participants (approximately 75 participants at each site)

Treatment Regimen	Participants will be provided with a supply of FTC/TDF tablets, taken orally, once daily for first 3 months. Thereafter, these tablets will only be supplied to those who indicate willingness to take PrEP and who do not have a clinical contraindication to do so.

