The rationale for this study design is based on some of the feedback received from the VOICE and FEMPREP studies. Women in these studies reported high PrEP usage, remained in study and yet drug levels indicated very poor PrEP usage (Marazzo et al CROI 2013). Some rationale for this has been that PrEP acceptability was low, but with a keen perception among participants that study participation hinged on pill adherence. Thus, despite information that drug levels would be assessed, participants chose to report pill usage falsely. By making it very clear that trial participation does NOT hinge on PrEP usage (other than the first 3 months) we hope that we will get a more accurate assessment of real PrEP usage. We also hope that if participants really want to be taking PrEP, that adherence to product will persist. Other open label studies such as iPrEx OLE suggest this may be the case. By designing the study with an “opt out” arm we hope that we will create an authentic comparator group for participants taking oral PrEP (FTC/TDF) persistently and adherently, in order to assess any significant differences in adolescents taking oral PrEP (FTC/TDF) versus those who choose NOT to do so. We recognize that these may include demographic differences but may also include perceptions of risk, sexual activity, etc. In addition, we hope that this will give us a true sense of pill usage among this population- data that is currently unknown and required in order to more accurately model the impact of this intervention in this age group.

Both groups will be treated equally, except for administration of TDF/FTC therapy to those who select to include PrEP in their prevention package.

It was felt by the protocol team that the question of use and acceptability would best be answered by employing an open label design. The three month initial phase will mean that everyone will at least be exposed to 3 months of PrEP usage.

Adherence to medication can be measured in different ways depending on the condition and the

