for continuing or stopping PrEP. A short acceptability questionnaire will also be administered. This opportunity to “opt out” or “opt back in” will occur at 3 monthly visits until Week 36. Followup will continue until week 48. Those who opt out at a 3 monthly visit will be asked whether they wish to restart at the next 3 monthly visit. Participants will also be advised that they may “opt out” of PrEP in their prevention package at any scheduled visit or at any time in consultation with clinic staff. They will be expected to return all study product and will not be issued TDF/FTC. They may “opt back in” on a subsequent study visit if all eligibility criteria are met and after a negative HIV test is obtained. At each study follow up visit, participants will be asked to grade their adherence on a visual scale, they will also be asked whether they wish to receive drug levels and their response and reasons for this will be captured. They will then receive motivational adherence counseling with or without drug levels depending on their choice at the time. Monthly scheduled visits will occur until month 3, thereafter scheduled visits will be 3 monthly.

Whilst every effort will be made to encourage adherence to PrEP in the first 3 months, poor adherence during those months will NOT preclude participation after 3 months. Every effort will be made to ascertain level of use and reasons for less than optimal use.

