The second focus group will be conducted in two groups with enrolled participants (n= 6-8 in each separate group) at each site, to be scheduled in the last four weeks of study follow up. It will address a number of questions including participants' attitudes towards PrEP, in particular, their experience taking and general acceptability of the drug; where they would like to access these drugs in the future; whether taking PrEP resulted in identification of individuals as high-risk and stigmatization; whether enhanced protection against HIV infection provided by PrEP led to sexual disinhibition or risk compensation; whether participants still used condoms in order to protect against other STI's; and what factors (such as appearance changes as a result of drug side-effects) impacted on adherence. In addition, they will be asked what the impact of real time (whilst this does not mean on the day of testing, it is used to denote during the study at the next visit) drug levels were in terms of adherence counseling and how they felt about receiving these results at study visits. This data will inform the nature of design of PrEP roll out for youth in the future. Parental/ guardian consent and adolescent assent will be obtained for all focus group participants. In order to ensure a good spread of FG participants, the follow up cohort will be divided into 2 groups: those who chose PrEP and were adherent at least 80% of the follow up time and those who did not choose PrEP or were adherent <50% of the time. 6-8 participants will be randomly selected from each group and then invited to participate in the 2 FGs. The data from these focus groups may be reviewed by Research Ethics Committee members, Data Safety Monitoring Committee members and the sponsors (NIAID), FDA and/or MCC.

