7.4 FOLLOW UP VISITS (AFTER WEEK 13 AND UP TO WEEK 48; VISITS AT 24, 36, 48)

For the initial product usage lead-in period (Weeks 4-12), study participants will be asked to adhere to the study product. After the 12 week lead in period, participants will be asked at subsequent 12 weekly visits whether they wish to continue PrEP, stop PrEP or restart PrEP as part of their prevention package (Week 12, 24 and 36). All participants regardless of product usage will be followed for the duration of the study. Participants will be advised to make these decisions at scheduled study visits. Reasons for decision will be enquired upon and recorded in CRFs.

Participants will also however be told they can contact study site at any time and also when they should with-hold PrEP for medical reasons.

Participants will complete scheduled 4 weekly follow-up visits until week 12. Thereafter, all visits will be 12 weekly regardless of PrEP addition to the prevention package or not. Target dates are set based on the enrollment date, and do not change if subsequent actual visits take place before or after the target date.

As it will not always be possible to complete follow-up visits on the targeted dates, follow-up visits may be completed within an approximate 2-week window around the target date (-/+7days from the target date).

The following procedures will be completed at each Follow-Up Visit (wks 24, 36, 48):

- Administrative/Behavioural Procedures
 - Locator information (update)
 - At all visits
 - HIV pre-and post-test counseling, including risk reduction counselling
 - At all visits
 - Social harms and/or benefits
 - At all visits
 - Sexual risk behavior questionnaire

- At all visits
- Provision of condoms
 - At all visits
- Provision of study drug (for participants who choose to receive study product)
 - at visits Wk 12, 24, 36 .
- Acceptability assessment
 - at visits Wk 12, 24, 36, 48.
- Adherence Counselling (if participant is on study product)
 - at visits Wk 12, 24, 36, 48 (week 48 visit will be feedback on last 3 months only since no more product will be offered).
- Feedback of plasma drug level/DBS results (to participants on study product who agree to receive this information at the time of adherence counseling.)
 - At visits Wk 12, 24, 36, 48.
- Adherence assessment (including pill counts) and counselling (for participants who choose to receive study product)
 - At visits Wk 12, 24, 36, 48

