7.10.4 Participants Who Temporarily Hold or Discontinue Product Use (Initiated by Participant)

For participants who independently choose to discontinue use of the study product (either temporarily or permanently), the protocol-specified visit schedule will be followed (for participants who choose to be maintained in follow-up), with the exception of administration of study product.

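### Section 9.7 lists repeated product non-compliance and pregnancy as grounds for ending study participation, against the protocol's own follow-up rules

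*Protocol*

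**What the plan says.** Protocol section 9.7 has two lists. The first gives criteria for permanently stopping product, and pregnancy/lactation is on it. The second gives criteria for ending study participation early. It contains "Participant repeatedly non-compliant with study product as prescribed" and lists pregnancy/lactation again. It does not say whether its criteria are mandatory or left to the site.

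Elsewhere, follow-up does not depend on taking the product:

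- Protocol summary, Design: "Participants will be followed regardless of PrEP usage for a total of 12 months (52 weeks").
- Section 7.4, on visits after week 12: "All participants regardless of product usage will be followed for the duration of the study".
- Section 4.1, on the three-month lead-in: "poor adherence during those months will NOT preclude participation after 3 months".
- Section 4.1, on the closing focus groups of enrolled participants: one of the two pools is "those who did not choose PrEP or were adherent <50% of the time".
- Section 7.10.4, on those who choose to stop product: "the protocol-specified visit schedule will be followed (for participants who choose to be maintained in follow-up), with the exception of administration of study product".

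Section 2.5 gives the reason. It reports from earlier trials a "keen perception among participants that study participation hinged on pill adherence", connects this with false reports of pill use, and answers it by making clear that "trial participation does NOT hinge on PrEP usage (other than the first 3 months").

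On pregnancy, sections 7.10.2 and 9.3 stop the product and keep the participant under observation to delivery or until the outcome is known. Section 7.10.2 limits the regular visit schedule to those who choose to stay.

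The SAP (Primary: Use) defines remaining on PrEP as any self-reported use, whatever the adherence. It censors for loss to follow-up and adds an analysis that treats those lost as non-adherent.

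**The concern.** Staff cannot follow both sets of instructions. If a site applied the non-compliance entry, follow-up would end for a reason tied to what the study sets out to measure, and it would end for the participants about whom the use and adherence endpoints have most to say. It would also work against the rationale in section 2.5.

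If a site applied the pregnancy entry, it would end the follow-up that sections 7.10.2 and 9.3 require. Adverse-event collection and expedited reporting are both tied to continued participation, so active reporting could stop before the birth outcome.

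Retention is itself among the primary endpoints in section 10.2, so every such exit also lowers a reported figure.

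**Working it through.** The point is mainly one of wording, so the check sets the texts side by side. The plan's one related figure is then reproduced.

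**1. The two entries against the rest of the protocol**

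| Entry in the 9.7 participation list | What the other sections require | Reconciled anywhere? |
|---|---|---|
| Repeated product non-compliance | Follow-up for 52 weeks whatever the use (summary, 7.4); poor lead-in adherence no bar (4.1); poor adherers still enrolled at the end (4.1, focus groups) | No |
| Pregnancy/lactation | Product stopped, follow-up to delivery or outcome (7.10.2, 9.3) | No |

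Pregnancy/lactation is already on the product-stop list. Its second appearance therefore adds only the study exit that 7.10.2 and 9.3 exclude.

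**2. Whom the non-compliance entry reaches.** A participant who has opted out has no product prescribed and stays on the visit schedule under 7.10.4. The entry therefore mainly reaches those who stay on PrEP but take it poorly. It can also cover over-use or sharing, since both depart from the prescription.

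**3. The three-month exception in 2.5.** This does not remove the conflict. Section 4.1 says that poor adherence in those same months does not bar later participation.

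**4. Pregnancy and the reporting windows.** Section 8.1 collects adverse events until the participant terminates. Section 8.2 ends expedited reporting at study completion or at discontinuation for any reason; after that, only SUSARs learned of passively are reported. Section 8.3 (i) makes a congenital anomaly an SAE criterion. Ending participation at pregnancy would therefore close active reporting before that criterion could be assessed.

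Deleting the entry does not fully cure this. With g weeks from conception to delivery, a conception after study week 52 − g delivers after week 52. For an assumed g = 38, that is any conception after week 52 − 38 = 14. Each week's change in g moves the cut-off by one week.

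**5. Classification in the SAP.** The SAP's censoring refers to loss to follow-up. Section 9.7 lists loss to follow-up separately from the two entries. The SAP therefore does not say whether investigator-ended participation is censored or enters the analysis that treats those lost as non-adherent.

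**6. Sample size (10.4).** Inputs: 135 evaluable and at most 10% premature censoring. 135 / (1 − 0.10) = 150, which matches the plan. The exact 95% interval has as its lower limit the 2.5% quantile of Beta(x, n − x + 1) and as its upper limit the 97.5% quantile of Beta(x + 1, n − x). For 14/135 this gives 5.8 to 16.8%, against 5.7 to 16.8 in the plan's table.

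The 10% allowance names loss to follow-up and withdrawal of consent, not investigator-ended participation. The documents give no rate for the latter. Assumed rates w on top of the 10% leave n = 150 × (1 − 0.10 − w). At a frequency of 10%, with x = 0.10n unrounded:

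| Assumed w | n left | Exact 95% interval |
|---|---|---|
| 0 | 135 | 5.5 to 16.3% |
| 5% | 128 (127.5 rounded) | 5.4 to 16.6% |
| 10% | 120 | 5.3 to 16.8% |
| 20% | 105 | 5.0 to 17.4% |

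Precision barely moves. What matters is who leaves, not how many.

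**The case against.** The best defence is that the specific sections govern. Sections 7.10.2 and 9.3 deal with pregnancy directly, and if sites follow them no reporting is lost. The statements about use in the summary and 7.4 can be read as concerning opt-outs, whom the 9.7 entry does not touch. Section 7.6 provides week-48 procedures at withdrawal and a week-52 visit if possible. The SAP already examines reasons for discontinuation and compares those lost with those retained. All of this limits the harm. None of it reconciles the texts: 9.7 still instructs otherwise, and the focus-group plan in 4.1 expects poor adherers to be enrolled at the end.

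One objection changes the remedy. Because non-compliance with the prescription also covers over-use and sharing, the entry has a possible safety purpose. Sections 2.5 and 6.4 provide for staff to act on levels suggesting over-use, and 6.4 and 13.3 counsel against sharing. Deletion should say where those cases go.

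Four stronger readings are tempting but not supported:

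- *The use estimate is biased by a known amount or in a known direction.* No exit rate is given. A poor adherer who reports any use counts as on PrEP under the SAP, so an exit may remove a user or a future stopper.
- *The effect can be bounded by counting every exit as off PrEP and then as still on it.* The number of exits is unknown. The second case is doubtful because tablets come through the study pharmacy (6.3.1).
- *The entry restores the incentive to over-report.* That is possible. But the mechanism in 2.5 works through what participants perceive, and 9.7 is addressed to staff. The documents reviewed do not show that participants are told of it.
- *Section 9.4 and the other compliance item in 9.7 open the same route.* Section 9.4 concerns study procedures, not product. The 9.7 item applies only where non-compliance would harm the participant or seriously threaten the validity of results.

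**Conclusion.** Wrong as written. The participation list in 9.7 contains two entries that the rest of the protocol contradicts, and no text resolves the conflict. Applied as written, the first would remove participants for a reason tied to the use and adherence endpoints, and the second could end active safety reporting before a birth outcome.

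No size or direction of bias is claimed, because the documents give no rate for either exit. The consequences assume that a site acts on the list rather than on the sections that contradict it. The pregnancy entry is a matter of safety follow-up and retention; it does not distort the use estimate, since the product stop is already a dated event. The sample size stands at 150.

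**What to change.** **Protocol**

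- In 9.7, delete the non-compliance and pregnancy/lactation entries from the participation list. Keep pregnancy/lactation on the product-discontinuation list.
- Add to 9.7: *Taking too few doses, or not using the product, is not by itself grounds for ending study participation. Over-use or sharing is managed by holding or stopping product under the existing safety procedures.*
- Add to 9.3: *Follow-up to pregnancy outcome, including reporting of any congenital anomaly, continues past week 52 where needed.* Make the reporting period in 8.2 consistent with this.

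**SAP**

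- Report any investigator-ended participation by reason and site.
- Include it in the planned sensitivity analysis that treats those lost to follow-up as non-adherent.

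**Cost.** A small protocol amendment with the ethics, regulatory and registration steps in 13.1 and 13.2, and a short SAP addition. Some pregnancies will need outcome follow-up after week 52, which 9.3 already implies. N stays 150.
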